## **Effect of Continuous Positive Airway Pressure (CPAP) treatment on cognitive ability in HIV+ individuals with obstructive sleep apnea (OSA): A pilot study**

CAM score and C3Q. The analysis will focus on estimating the proportion of responders. A sample size of 30 participants will provide sufficient power for within-group analysis. With the assumption that the outcome is drawn from a binomial distribution with an expected probability of response of 10% (N=3) with no intervention, 30 subjects in the intervention group will allow detection of a positive response, with 80% power and  $p<0.05$ , if 7 or more persons respond (stattrek.com binomial calculator.) The proportion of responders on the different cognitive outcomes will also be estimated.

A secondary analysis will relate adherence to CPAP to change in cognitive outcomes using linear regression adjusting for age, sex, weight, baseline sleep satisfaction.

For between-cohort comparisons of cognitive outcomes, generalized estimating equations (GEE) will be used to permit both the baseline and post-intervention measures to be included along with the within-person correlation. A linear GEE will be used as the outcomes are continuous although a binary response was used for the primary objective. The model will include the indicator variable for cohort (CPAP, refuser, or control), time (assessment 1, 2), as well as confounding variables of age, sex, education, BMI, and comorbidity. As the control cohort will be very much larger than the intervention cohort, statistical comparisons have sufficient power to detect effect sizes of 0.5 or greater, suitable for a pilot study. The parameter estimated from GEE is equivalent to an adjusted effect size (adjusted between cohort effect divided by correlation adjusted standard error).

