**PROTOCOL SUMMARY**

Full Title	Effect of Continuous Positive Airway Pressure (CPAP) treatment on cognitive ability in HIV+ individuals with obstructive sleep apnea (OSA): A pilot study
Short title	HIV and CPAP
Sponsor	McGill University
Funding	Canadian Institute of Health Research (CIHR) CPAP and masks for the duration of the study are provided in-kind by Resmed and cost of visits related to its initiation and calibration are provided in-kind by VitalAire
Principal Investigators	[name], [name], [name]
Associate investigators	[name], [name]
Objectives	
The primary objective is to estimate among people with HIV and obstructive sleep apnea, the extent to which 4-7 months of CPAP impacts on the primary outcome of cognitive ability (B-CAM), in comparison to individuals who screen positive for OSA but are not participating in the sleep apnea intervention.
 
An exploratory objective is to identify whether the changes are similar on measured cognitive ability and on self-reported cognitive symptoms.
 
The explanatory objective is to relate degree of adherence to CPAP to change in cognitive outcomes.

Study Population	
Inclusion Criteria
 

• Participants in the cohort study “Understanding and Optimizing Brain Health in HIV Now”

• Screened positive for OSA using the Berlin or the STOP-BANG (completed as part of the main study visits)

• Have been on a stable HAART regimen for > 6 months

• B-CAM ≤ 29

• Have not had a change in medications that could potentially interfere with sleep or cognition in the past 4 months.

• Willing to use CPAP as per instructions

• Able to comply with follow-up visit assessments

• Able to communicate in English or French

• Have at least one remaining visit in the main cohort study

 
Exclusion Criteria
 

• Already treated for OSA

**Effect of Continuous Positive Airway Pressure (CPAP) treatment on cognitive ability in HIV+ individuals with obstructive sleep apnea (OSA): A pilot study**

	

• Ongoing involvement in night shift work

• Presence of restless legs syndrome requiring immediate specific treatment

Study Design	Quasi-experimental single-arm, pre-post design will be carried out over a period of 4-7 months.

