### **STUDY OBJECTIVES**

The overall aim is to contribute evidence about the impact of treatment of sleep apnea (with CPAP) on cognitive ability in HIV+ individuals.

The primary objective is to estimate among people with HIV and obstructive sleep apnea, the extent to which 4-7 months of CPAP impacts on cognitive ability (B-CAM), in comparison to individuals who screen positive for OSA but are not participating in the sleep apnea intervention.

An exploratory objective is to identify whether the changes are similar on measured cognitive ability and on self-reported cognitive symptoms.

The explanatory objective is to relate degree of adherence to CPAP to change in cognitive outcomes.

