### **STUDY HYPOTHESIS**

Given there is no expectation for improvement in cognitive ability in this population in the absence of treatment for sleep apnea, we hypothesize that, over 4-7 months weeks of CPAP use, an improvement in cognition will occur, and if this is observed in 7 or more of 30 people, this response frequency is unlikely to have occurred by chance.

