### **STUDY DESIGN**

This study is part of a larger project based upon a cohort multiple randomized controlled design [29]. Within a fully characterized cohort (N=840) which is followed over time, people meeting the specific criteria for one or more interventions (here CPAP) are identified and a sample is randomly selected to receive the intervention; the remaining eligible persons who do not receive the intervention serve as controls. This design, when operationalized for one intervention, yields three cohorts: (i) the intervention cohort comprising all those approached who agreed to enter; (ii) the refuser cohort comprising all those approached who declined entry; and (iii) control cohort comprising eligible persons who were not approached, and hence were not given the opportunity to accept or decline. For the CPAP intervention, the duration of the study is 4-7 months.

Eligible patients will be identified among the Montreal participants (N=500) in the “Understanding and Optimizing Brain Health Now” cohort study who have screened positive for the possible presence of sleep apnea on either the Berlin or the STOP-BANG and experience some cognitive difficulties as measured by the B-CAM ( $\leq 29$ ). We will continue recruitment until 30 participants have used the CPAP device for a minimum of 4 months, on at least 30% of the nights with a median of  $\geq 4$  hours/night.

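### The primary objective compares CPAP with non-participants, but the hypothesis and sample-size rule attached to it are a within-group count of 7 in 30 against an unsourced 10%, and the protocol does not say that its planned between-cohort model answers the objective

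*Protocol*

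**What the plan says.** The Protocol Summary and Study Objectives set the primary objective as the effect of CPAP on B-CAM "in comparison to individuals who screen positive for OSA but are not participating in the sleep apnea intervention". Study Design supports a comparison: within the cohort "a sample is randomly selected to receive the intervention; the remaining eligible persons who do not receive the intervention serve as controls", and Measurement lists intervention, refuser and control cohorts to be compared.

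Other parts describe a one-group study. The Protocol Summary gives the design as "Quasi-experimental single-arm, pre-post design will be carried out over a period of 4-7 months". Study Hypothesis rests on a count in treated people: "if this is observed in 7 or more of 30 people, this response frequency is unlikely to have occurred by chance". Statistical Analysis and Sample puts the focus on the proportion of responders (improvement of half an SD), justifies 30 participants for a within-group analysis, and takes its null as follows: "With the assumption that the outcome is drawn from a binomial distribution with an expected probability of response of 10% (N=3) with no intervention". The only reference given there is a web binomial calculator.

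The same section then plans a between-cohort model: "A linear GEE will be used as the outcomes are continuous although a binary response was used for the primary objective". On its terms it says: "The model will include the indicator variable for cohort (CPAP, refuser, or control), time (assessment 1, 2", followed by adjustment covariates. It states adequate power for effect sizes of 0.5 or more because the control cohort will be much larger, without giving the number of controls.

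**The concern.** The objective asks how B-CAM under CPAP differs from B-CAM without it. The decision rule asks whether the treated group's response proportion exceeds a fixed constant. The rule makes no use of the control cohort, which is the study's own source for the response rate without CPAP. Its claim about chance therefore depends wholly on the 10%.

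The protocol says the pilot will inform a larger study. As written, 7 responders in 30 could be reported as meeting a comparative objective although the rule applied contains no comparison. With a GEE also planned and its role unstated, two analyses could give different answers to the primary question, and the protocol does not say which one governs.

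**Working it through.** **Inputs from the protocol** (Statistical Analysis and Sample): n = 30, threshold 7, untreated rate 10%, p<0.05. Not given: a source for the 10%, the response rate assumed under CPAP, the number of controls, and the B-CAM retest correlation.

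**1. The plan's own threshold.** With X ~ Binomial(30, 0.10):
- P(X ≥ 7) = 0.0258
- P(X ≥ 6) = 0.0732

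Seven is the smallest count with a one-sided p below 0.05, so the threshold reproduces. The 80% power stated with it cannot be checked, because no response rate under CPAP is given. It would require a true rate of about 28.7%. The point made here does not rely on this.

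**2. Sensitivity of the rule to the 10%.** P(X ≥ 7) with n = 30:

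| Untreated rate | Chance of 7 or more |
|---|---|
| 10% | 2.6% |
| 11.5% | 5.0% |
| 15% | 15.3% |
| 20% | 39.3% |
| 25% | 65.2% |

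At exactly 7 of 30 (23.3%) the exact 95% interval is 9.9% to 42.3%.

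**3. Can the protocol settle the untreated rate?** It cannot. As an illustration, assume normal scores, no true change and a cut of 0.5 baseline SD. With retest correlation r, the SD of change is √(2(1−r)), and the chance of response by noise alone is 1 − Φ(0.5/√(2(1−r))).
- B-CAM alone, r = 0.9: SD 0.447, z = 1.118, rate 13%.
- B-CAM alone, r = 0.8: SD 0.632, z = 0.791, rate 21%.
- B-CAM alone, a rate of 10% needs r of about 0.92.
- Response required on both B-CAM and C3Q, r = 0.7 to 0.8 on each, correlation between the two change scores 0 to 0.3: rate about 5% to 10%.

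So 10% may be too low on one reading of response, and about right or cautious on the other.

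**4. Which analysis is tied to the objective?** The GEE is the only planned analysis that contains the control cohort. The sentence introducing it says a binary response was used for the primary objective and so sets the GEE apart. The section never calls the GEE primary or secondary; the only analysis it labels secondary is the adherence regression.

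**5. Would the comparison be workable?** Use a two-sided z-test at 0.05 on mean change, with SE = √(2(1−r)) × √(1/n₁ + 1/n₀) in baseline SD units. Example: n₁ = 30, n₀ = 150, r = 0.5 gives SE = 1 × √(1/30 + 1/150) = 0.200, z = 0.5/0.200 = 2.5, power 71%. The number of controls is assumed; the source population is given as: "Eligible patients will be identified among the Montreal participants (N=500".

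| Treated, mean effect | Controls | r = 0.5 | r = 0.7 | r = 0.8 |
|---|---|---|---|---|
| 30, 0.5 SD | 150 | 71% | 90% | 98% |
| 30, 0.5 SD | 60 | 61% | 82% | 94% |
| 43, 0.35 SD | 150 | 53% | 74% | 89% |
| 60, 0.25 SD | 150 | 37% | 56% | 74% |

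The last two rows illustrate dilution when everyone who agreed to enter is analysed. They assume 30 people gain 0.5 SD and the rest gain nothing (0.5 × 30/43 = 0.35; 0.5 × 30/60 = 0.25). The 43 and 60 are assumptions.

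**The case against.** The strongest reply is that the comparison is already planned. Measurement says the cohorts will be compared, and the analysis section gives that comparison a model, covariates and a power statement. The clause about the binary response could merely explain a change of outcome scale. This stands in part: a reader might infer that the GEE has been demoted to secondary, or that no comparison will be made, and the text says neither. What remains is that the protocol does not say the GEE answers the primary objective, and its wording points away from that.

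Second, the 10% is openly an assumption in a pilot. That also stands. A reader might infer from the error rates above that the false-positive rate is inflated. The document has no retest data, and if response means improvement on both measures, 10% may be adequate.

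Third, the responder sentence, which names B-CAM and C3Q together, might be read as contradicting the sentence before it, which classifies on B-CAM. It can equally mean that the same half-SD cut applies to each measure separately, so this is an ambiguity.

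Fourth, a reader might infer that the GEE would halve the effect because no cohort-by-time term is listed. A model with main effects only would do so (with equal baselines, (0 + 0.5)/2 = 0.25 SD), but the protocol does not commit to that fit, and an analysis plan commonly supplies such detail.

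Finally, response proportion and adherence suit the pilot's feasibility aim, and the comparison may have modest power. Both are fair. They are reasons to report an estimate with its interval, but they do not make a one-group count an answer to a comparative objective.

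**Conclusion.** The point holds as a mismatch between the stated primary objective and the rule attached to it, and it should be fixed. The objective is between cohorts; the hypothesis, the sample size and the claim about chance are within one group, against an unsourced 10%. That follows from the text and needs no assumption.

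The claim about chance has little margin: it holds at the one-sided 5% level only for an untreated rate up to about 11.5%. Whether the true rate lies above or below that cannot be decided from the protocol. That the GEE is not the primary analysis is an inference from wording and should be put as an unclear assignment. The power figures rest on assumed control numbers, retest correlations and effect sizes.

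**What to change.** - In Study Hypothesis and in Statistical Analysis and Sample, state that the planned between-cohort GEE on B-CAM answers the primary objective. Name the cohort-by-time contrast (difference between cohorts in change from assessment 1 to 2) as the estimate, with its confidence interval.
- Keep the responder proportion as a supportive and feasibility measure, with its interval, beside the control-cohort proportion over the same visit interval.
- Drop the claim that 7 of 30 is unlikely by chance, or take its null rate from the control cohort.
- State that B-CAM response and C3Q response are classified separately.
- Align the design label in the Protocol Summary with Study Design.

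Eligible controls, scheduled-visit outcomes and refusers in the model are already in the protocol, so no new data are needed. The cost is a restated sample-size justification and the loss of the fixed 7-of-30 claim. For 30 treated and 0.5 SD, the assumed power range is 71% to 98% with 150 controls and 61% to 94% with 60. It is lower if everyone who agreed to enter is analysed and some make little use of CPAP. The expected number of controls and the assumed correlation should be stated.

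### The 80% power claim is tied to the rejection threshold of 7 of 30; if the true response rate were 7/30, power would be 57%

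*Protocol*

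**What the plan says.** The Statistical Analysis and Sample section of the protocol asserts that "A sample size of 30 participants will provide sufficient power for within-group analysis". Its basis is a binomial outcome with an "expected probability of response of 10% (N=3) with no intervention". From this it concludes that "30 subjects in the intervention group will allow detection of a positive response, with 80% power and" p<0.05, "if 7 or more persons respond", and cites an online binomial calculator.

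The Study Hypothesis section uses the same count as a test against chance: "if this is observed in 7 or more of 30 people, this response frequency is unlikely to have occurred by chance".

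Neither section gives a true response rate under CPAP at which the 80% was computed, and neither says whether the 5% level is one-sided or two-sided.

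**The concern.** Power is the probability of meeting the success rule when the true response rate takes some stated value. The protocol instead makes its 80% conditional on the observed count that triggers success. Once 7 people have responded, the rule is met and there is no power left to state. The hypothesis section confirms that 7 of 30 is a rejection rule under the 10% null and not an assumed effect of CPAP.

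This calculation is the only basis given for the number 30. A reader who takes the 80% at face value will think the study well placed to detect a response rate of about 23%, and may read 6 or fewer responders as fair evidence against such a rate. The protocol's section on anticipated results says that the proportion responding will help judge whether further CPAP research is warranted, so the chance of a false negative matters for that judgement.

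**Working it through.** **Inputs, all from the protocol**
- n = 30, a single group (Statistical Analysis and Sample). No dropout allowance is applied, because the Study Design section says "We will continue recruitment until 30 participants have used the CPAP device for a minimum of 4 months" at the required level of use.
- Null response rate p0 = 0.10 (3/30), binomial outcome.
- Success if X ≥ 7; level 0.05, sidedness not stated.
- Stated power 80%; true response rate under CPAP not stated.

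**Formula**

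P(X ≥ r | n, p) = 1 − Σ C(n,k) p^k (1−p)^(n−k), summed over k = 0 to r−1. With p = 0.10 this is the type I error; with p equal to the true rate under CPAP it is the power.

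**Step 1: the p<0.05 part reproduces**
- P(X ≥ 6 | 30, 0.10) = 1 − 0.9268 = 0.0732, above 0.05.
- P(X ≥ 7 | 30, 0.10) = 1 − 0.9742 = 0.0258, below 0.05.

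Seven is therefore the one-sided 5% critical value, and lowering it to 6 would exceed 5%. Doubling the tail gives 2 × 0.0258 = 0.0516, so a two-sided reading by that convention would just miss 0.05.

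**Step 2: the 80% does not reproduce at 7/30**

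The only rate that the sentence can be read as implying is 7/30 = 23.3%, which is taken here as an assumption:

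P(X ≥ 7 | 30, 7/30) = 1 − 0.4296 = 0.5704, so power is 57% and the miss rate 43%.

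**Step 3: power of the 7-of-30 rule over a range of true rates (exact)**

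| True response rate | Power |
|---|---|
| 20% | 39.3% |
| 23.3% (7/30) | 57.0% |
| 25% | 65.2% |
| 28% | 77.6% |
| 28.7% | 80.0% |
| 30% | 84.0% |
| 33.3% | 91.6% |

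Solving P(X ≥ 7 | 30, p) = 0.80 gives p = 0.287, which is 0.287/0.10 = 2.9 times the null rate.

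**Step 4: could another method have given 80% at 7/30?**

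| Method | One-sided | Two-sided |
|---|---|---|
| Normal approximation | 71.2% | 63.2% |
| With continuity correction | 63.5% | 54.8% |
| Arcsine | 63.8% | 51.5% |
| Wald | 53.3% | 40.8% |
| Null variance used throughout | 78.5% | 68.2% |

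Only the last method, one-sided, comes near 80%. It applies the variance of a 10% rate to a 23.3% rate and is not the binomial calculation that the protocol cites.

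**Step 5: what 80% at 7/30 would need**

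Increasing n from 30, with the smallest threshold that keeps one-sided type I error at or below 5%, exact power at 7/30 first reaches 80% at n = 47 with success at 9 or more: P(X ≥ 9 | 47, 0.10) = 0.041 and P(X ≥ 9 | 47, 7/30) = 0.800.

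**The case against.** The strongest reply is that the protocol names no alternative rate, so its 80% is unspecified and not refuted. The design does deliver 80% at a true rate near 28.7%, and 84% at 30%. On this view the 57% rests on a rate that the protocol never asserts, and it is awkward to call 7 a critical value and then compute power at 7/30.

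This is correct as far as it goes: 57% is conditional on 7/30, and the table in the working is the full answer. It does not rescue the sentence. The protocol prints a definite power figure and attaches it to a count that, read as a threshold, cannot carry a power and, read as a true rate, gives 57%. The rate at which 80% would be right appears nowhere.

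Four narrower points stand:
- The origin of the 80% cannot be recovered from the document. The null tail explains the p<0.05 but not the 80%.
- The same section also claims adequate power for the between-cohort comparison, so the 7-of-30 calculation is the only stated basis for the number 30 but not the only power argument.
- The protocol sets no futility rule for fewer than 7 responders and says that the analysis centres on estimating the proportion. Misreading a low count is thus a risk, not a planned step.
- The rule is plainly upper-tailed. A two-sided exact p-value by the minimum-likelihood method is also 0.026, because under the null P(X=0) = 0.042 exceeds P(X=7) = 0.018. Stating sidedness is a clarification.

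That this is a pilot, and that the correction is one of wording, limits the consequences. It does not make the figure right.

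**Conclusion.** The concern holds. Seven of 30 is a valid one-sided threshold against a 10% null, with type I error 2.6%. The 80% power attached to it is unsupported as written. Power is 57% if the true response rate is 7/30, between 39% and 65% for true rates of 20% to 25%, and 80% only at about 28.7%.

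These figures assume the protocol's own binomial model, 30 evaluable participants, the 10% null rate and a one-sided test. The 57% further assumes a true rate of 7/30, which the protocol suggests but does not state. The success rule, type I error and enrolment target are unaffected.

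**What to change.** Replace the power sentence in Statistical Analysis and Sample with wording such as: With 30 participants, a null response rate of 10% and success defined as 7 or more responders, the one-sided type I error is 2.6%; power is 80% if the true response rate is about 29%, and 57% if it is 23%. State that the test is one-sided, and make the same clear in the Study Hypothesis section, so that 7 of 30 reads as the decision threshold.

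The cost is a change of wording and a less favourable power statement; enrolment, conduct and analysis stay as they are. Only if the sponsor wants 80% power at a true rate of 23.3% would the sample have to grow, to about 47 with success at 9 or more.

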## **Effect of Continuous Positive Airway Pressure (CPAP) treatment on cognitive ability in HIV+ individuals with obstructive sleep apnea (OSA): A pilot study**

- Screen positive for the presence of OSA with either the Berlin or the STOP-BANG
- Have been on a stable HAART regimen for > 6 months
- B-CAM score ≤ 29
- Have not had a change in medications that could potentially interfere with sleep or cognition in the past 4 months.
- Willing to use CPAP as per instructions
- Able to comply with follow-up visit assessments
- Able to communicate in English or French
- Have at least one remaining visit in the main cohort study

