### **Screening:**

Brain Health Now study participants who screen positive for the presence of OSA, meet inclusion/exclusion criteria based on the information already available as part of the main study questionnaires and who, on initial enrolment, have agreed to be contacted for sub-studies, will be approached for participation. Those who agree to participate and provide informed consent will be referred for a polysomnography (sleep study). Those with confirmed OSA will continue to the intervention phase.

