### **Intervention (CPAP)**

Participants will be evaluated by a sleep specialist who will confirm eligibility for CPAP treatment. Eligible participants will be referred to VitalAire for initiation of treatment, following a standard protocol for use in the home (see Appendix 2). CPAP treatment will continue until the next visit for the main study, between 4-7 months based on the timing of the evaluations, after which the OSA study will end.

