## **Effect of Continuous Positive Airway Pressure (CPAP) treatment on cognitive ability in HIV+ individuals with obstructive sleep apnea (OSA): A pilot study**

The values to be used will be those collected during the scheduled platform evaluations which occur 9-12 months apart.

- (ii) Self-reported cognitive symptoms will be measured using the C3Q (Communicating Cognitive Concerns in HIV) collected during the scheduled platform evaluations which occur 9-12 months apart.
- (iii) Adherence to the CPAP home treatment will be obtained from the CPAP device directly through its telemonitoring function, which is done by activating modems on CPAP machines and having the data transferred onto the Compliance Management Solutions. The granularity of the data will yield a continuous metric of sleep-minutes of use. Reasons for poor adherence and tolerance will be obtained by telephone contact or at clinical visits with the sleep specialist.
- (iv) Three cohorts will be compared: (i) the intervention cohort comprising all those approached who agreed to enter; (ii) the refuser cohort comprising all those approached who declined entry; and (iii) control cohort comprising eligible persons who were not approached, and hence were not given the opportunity to accept or decline.

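### Entry is selected on B-CAM but not on C3Q, so the within-arm responder proportions on the two measures have different, unknown no-effect values and should not be read against each other for the exploratory objective.

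*Protocol*

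**What the plan says.** Study Objectives: "An exploratory objective is to identify whether the changes are similar on measured cognitive ability and on self-reported cognitive symptoms". No analysis is tied by name to this objective.

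Statistical Analysis and Sample defines a responder by a half-SD improvement on B-CAM and C3Q. It does not say which SD, or whether the two measures count jointly or separately. It then adds: "The proportion of responders on the different cognitive outcomes will also be estimated". The same section plans a linear GEE comparing the CPAP, refuser and control cohorts on the cognitive outcomes. The listed terms are cohort, time and confounders.

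Inclusion criteria: "B-CAM score ≤ 29". No criterion refers to C3Q.

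Screening: those approached must "meet inclusion/exclusion criteria based on the information already available as part of the main study questionnaires".

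Measurement, on B-CAM: "The values to be used will be those collected during the scheduled platform evaluations which occur 9-12 months apart". On C3Q: "Self-reported cognitive symptoms will be measured using the C3Q (Communicating Cognitive Concerns in HIV) collected during the scheduled platform evaluations".

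Intervention (CPAP): "CPAP treatment will continue until the next visit for the main study, between 4-7 months based on the timing of the evaluations".

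Study Hypothesis: "Given there is no expectation for improvement in cognitive ability in this population in the absence of treatment for sleep apnea".

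**The concern.** A person who enters because a score fell at or below a cut-off tends to score higher next time, since part of the low score was measurement error. If the score that admitted the person is also the pre-treatment value, that rebound counts as improvement. B-CAM is exposed to this. C3Q is not selected on its own error, so it is not exposed in the same way.

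The two responder proportions would therefore start from different values under no CPAP effect. The Study Hypothesis expects no improvement without treatment, and the sample-size text uses one 10% no-intervention rate, so the protocol makes no allowance for this. An excess of B-CAM responders could be taken to mean that CPAP helps tested ability but not perceived cognition. Similar proportions could be taken as agreement when one of them is partly regression to the mean.

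**Working it through.** **1. The plan's own figure.** With n = 30 and a no-intervention rate of 10%, P(X ≥ 7) = 0.026 and P(X ≥ 6) = 0.073. Seven is thus the smallest count with one-sided p < 0.05, and the stated cut-off is reproduced. The 80% power cannot be checked because no alternative rate is given. At a true rate of 7/30 power is 57%, and 80% needs about 28.7%. This rule does not bear on how the two measures compare.

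**2. Is the qualifying score the baseline?** Screening uses cohort data already on file. Measurement takes outcome values from scheduled cohort visits. CPAP runs to the next such visit. The GEE has two assessments, and no separate pre-CPAP B-CAM is described. The visit before CPAP is then naturally both the qualifying and the baseline visit. This is an inference.

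**3. Model under no CPAP effect.** Baseline and follow-up are bivariate normal in cohort SD units, with test-retest correlation r. Entry takes the lowest fraction q on baseline B-CAM. A responder gains at least 0.5 cohort SD. The values of r (0.7 to 0.9) and q (0.3 to 0.7) are assumptions, because the protocol gives no mean, SD, reliability or share with B-CAM at or below 29.

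- C3Q, not selected on its own error: P = 1 − Φ(0.5/√(2(1−r))). For r = 0.8 this is 1 − Φ(0.5/0.632) = 1 − Φ(0.791) = 21.5%.
- B-CAM: P(follow-up − baseline ≥ 0.5, given baseline ≤ z_q), where z_q = Φ⁻¹(q), by numerical integration.
- Mean B-CAM drift: (1−r)·φ(z_q)/q. For r = 0.8 and q = 0.5 this is 0.2 × 0.798 = 0.16 SD. For C3Q it is 0.

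| r (both) | q | B-CAM responders | C3Q responders | Gap (points) | B-CAM drift (SD) |
|---|---|---|---|---|---|
| 0.7 | 0.3 | 41.7% | 25.9% | 15.7 | 0.35 |
| 0.7 | 0.5 | 36.1% | 25.9% | 10.2 | 0.24 |
| 0.7 | 0.7 | 31.8% | 25.9% | 5.9 | 0.15 |
| 0.8 | 0.3 | 33.0% | 21.5% | 11.5 | 0.23 |
| 0.8 | 0.5 | 28.9% | 21.5% | 7.4 | 0.16 |
| 0.8 | 0.7 | 25.7% | 21.5% | 4.3 | 0.10 |
| 0.9 | 0.3 | 19.1% | 13.2% | 5.9 | 0.12 |
| 0.9 | 0.5 | 17.0% | 13.2% | 3.8 | 0.08 |
| 0.9 | 0.7 | 15.4% | 13.2% | 2.2 | 0.05 |

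A milder cut (q = 0.85) leaves gaps of about 1 to 3 points. A B-CAM to C3Q correlation of 0.3 barely changes the results. If the half SD were that of the enrolled sample, truncation would shrink the B-CAM threshold and widen the gap: at r = 0.8 and q = 0.5, B-CAM becomes 40.8% against 21.5%.

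**4. Unequal reliability.** With r = 0.8 for B-CAM, 0.7 for C3Q and q = 0.7, the proportions are 25.7% and 25.9%, so there is no gap. With 0.9, 0.7 and q = 0.5 they are 17.0% and 25.9%, so the gap reverses. With no selection at all, 0.9 and 0.7 give 13.2% and 25.9%. Reliability alone moves the no-effect values.

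**5. Sampling error at n = 30.** Treating the two responses as roughly independent, the SD of the difference is √[(p_B(1−p_B) + p_C(1−p_C))/30]. At r = 0.7, q = 0.3: √[(0.243 + 0.192)/30] = 12 points. At r = 0.9, q = 0.7: √[(0.130 + 0.114)/30] = 9 points. In simulation over the nine table scenarios (true-score correlation 0.3), an exact McNemar test gave p < 0.05 in 2 to 17% of trials. C3Q responders equalled or exceeded B-CAM responders in 12 to 47%.

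**6. Control contrast.** Controls are described as eligible persons, so they meet the same B-CAM rule and share its no-effect rate (28.9% in both cohorts at r = 0.8, q = 0.5). The CPAP-minus-control difference then has expectation zero on B-CAM and on C3Q, if the cohorts are exchangeable and selected at the same visit.

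**The case against.** The strongest reply is that the protocol says the proportions will be estimated. It does not say that they will be compared or that they answer the exploratory objective. The objective speaks of changes, and details of an exploratory analysis may sit in an analysis plan not seen here. This stands as a limit on the point: the formal comparison is something a reader might infer, and the text does not state it. But these proportions are the only per-measure result named, and they are what readers will set side by side.

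A second reply is that the planned GEE already offers a controlled route. This also stands in part. A reader might infer that the objective cannot be answered at all, and the documents do not support that. However, the GEE is not tied to this objective, and the listed terms include no cohort-by-time interaction, so the model as listed does not estimate differential change.

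Third, a reader might infer that B-CAM must show more responders and that the pilot would draw a false conclusion. Steps 4 and 5 of the working show otherwise: direction depends on unknown reliabilities, and 30 participants give a noisy difference. That weakens any predicted error. It does not make the raw proportions interpretable.

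Two smaller cautions also hold. If the qualifying visit preceded the last pre-CPAP visit, some regression would be spent before baseline. C3Q may also be indirectly selected, because the OSA screen includes self-reported tiredness. A floor effect on C3Q cannot be argued, since the protocol gives no C3Q range or distribution.

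**Conclusion.** The concern holds in limited form. Selection on B-CAM but not on C3Q, with the qualifying score as baseline on the natural reading, gives the two within-arm proportions different and unknown no-effect values. Under equal reliability of 0.7 to 0.9 and selection of the lowest 30 to 70%, the artefact is about 2 to 16 points towards B-CAM. Unequal reliability can remove or reverse it. Neither a difference nor agreement between the raw proportions therefore says whether CPAP acts similarly on the two measures. The weight is moderate: the objective is exploratory and the study a pilot, but the repair is cheap and uses data already collected.

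**What to change.** In Statistical Analysis and Sample:

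- Tie the exploratory objective to the planned GEE, fitted separately to B-CAM and C3Q.
- Add a cohort-by-time term, and estimate the CPAP-versus-control difference in change among controls who meet the same B-CAM rule at the same visit.
- Divide each difference by that measure's baseline SD in the cohort, and compare the two with a confidence interval. The effect size now described divides by a standard error, which yields a test statistic and not a value in SD units.
- Keep the within-arm responder proportions as descriptive, and state that they are not to be read against each other.
- State which visit supplies the baseline B-CAM.

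The cost is analysis wording only, since both measures are collected at the cohort visits. Control-adjusted differences are less precise than raw proportions. The correction also assumes exchangeable cohorts. That needs acknowledging, because CPAP participants have confirmed OSA and the target of 30 counts those who reach a minimum level of use, whereas controls are only screen-positive.
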